5.2 Exclusion criteria

- 5.2.1 Evidence of uncontrolled, pulmonary infection
- **5.2.2** Subjects with unstable coronary insufficiency, severe cardiac arrhythmias, and/or uncontrolled hypertension.
- **5.2.3** History of hypersensitivity to propylene glycol

- **5.2.4** History of allergic reaction or hypersensitivity to Technetium- 99m sulfur colloid, used in lung deposition studies
- **5.2.5** ECOG performance status greater than or equal to 3
- **5.2.6** Serum creatinine >2.5 mg/dl
- **5.2.7** Documented allergy or intolerance to cyclosporine
- **5.2.8** Women pregnant or breast feeding or not willing to use an approved method of birth control
- **5.2.9** Inability to comprehend the investigational nature of the study and provide informed consent
- **5.2.10** Life expectancy less than 18 weeks
- **5.2.11** An increase \geq 5% and an absolute increase \geq 0.05 in FEV1 in the 18 weeks (minimum documentation of 3 weeks) preceding study enrollment
- **5.2.12** Subjects who have had prior administration of inhaled cyclosporine.

6.0 TREATMENT PLAN

6.1 **Pre-treatment Medication (albuterol)**

Subjects will receive metered dose inhaler albuterol, 2 puffs as needed for prevention of bronchospasm or 3 ml solution for nebulization. Subjects may receive levalbuterol in place of albuterol or not receive pre-treatment.

- **6.1.1 Inhalation device:** Subjects will be instructed regarding the use of the inhalation device as follows:
 - Shake the inhaler well.
 - Breathe out as completely as possible through your mouth.
 - Hold the canister with the mouthpiece on the bottom, facing you and the canister pointing upward. Place the open end of the mouthpiece into your mouth. Close your lips tightly around the mouthpiece.
 - Breathe in slowly and deeply through the mouthpiece. At the same time, press down once on the container to spray the medication into your mouth.
 - Try to hold your breath for 10 seconds, remove the inhaler, and breathe out slowly.
 - Wait 10 minutes before beginning cyclosporine nebulizer treatment.

6.1.2 Nebulizer: Subjects will be instructed regarding the use of the nebulizer device as follows:

• Before treatment, wash your hands with soap and water and dry completely.

- Place the air compressor on a sturdy surface that will support its weight. Plug the cord from the compressor into a properly grounded (three-prong) electrical outlet.
- Carefully measure medications exactly as you have been instructed and put them into the nebulizer cup.
- Assemble the nebulizer cup and mask or mouthpiece.
- Connect the tubing to both the aerosol compressor and nebulizer cup (with filter if beginning treatment with cyclosporine).
- Turn on the compressor to make sure it is working correctly. You should see a light mist coming from the back of the tube opposite the mouthpiece.
- Sit up straight on a comfortable chair. If the treatment is for your child, he or she may sit on your lap. If you are using a mask, position it comfortably and securely on you or your child's face. If you are using a mouthpiece, place it between you or your child's teeth and seal the lips around it.
- Take slow, deep breaths.
- Continue the treatment until the medication is gone (an average of 10 minutes for albuterol). The nebulizer will make a sputtering noise, and the cup will have just a little medication remaining.
- If dizziness or jitteriness occurs, stop the treatment and rest for about 5 minutes. Continue the treatment, and try to breathe more slowly. If dizziness or jitteriness continues to be a problem with future treatments, inform your doctor.
- During the treatment, if the medication sticks to the sides of the nebulizer cup, you may shake the cup to loosen the droplets.
- After each treatment, rinse the nebulizer cup thoroughly with warm water, shake off excess water, and let air-dry.
- Wait 10 minutes before beginning cyclosporine nebulizer treatment.
- 6.1.3 Concomitant Medications of Concern with albuterol (concurrent use will be per PI discretion and carefully monitored) Subjects will be queried as to what prescription medications, vitamins, nutritional supplements, and herbal products they are taking, or have stopped taking within the past two weeks as medication dose adjustments may be required or subjects carefully monitored for side effects with the following medications:
 - beta blockers such as atenolol (Tenormin), labetalol (Normodyne), metoprolol (Lopressor, Toprol XL), nadolol (Corgard), and propranolol (Inderal); digoxin (Lanoxin); diuretics; epinephrine (Epipen, Primatene Mist); other inhaled medications used to relax the air passages such as metaproterenol (Alupent) and levalbuterol (Xoponex); and medications for colds
 - antidepressants such as amitriptyline (Elavil), amoxapine (Asendin), clomipramine (Anafranil), desipramine (Norpramin), doxepin (Adapin, Sinequan), imipramine (Tofranil), nortriptyline (Aventyl, Pamelor), protriptyline (Vivactil), and trimipramine (Surmontil); and monoamine oxidase (MAO) inhibitors, including isocarboxazid (Marplan), phenelzine (Nardil), selegiline (Eldepryl, Emsam), and tranylcypromine (Parnate).
- **6.1.4** Subjects will also be instructed to discontinue albuterol and notify the research team immediately if they:
 - become pregnant, plan to become pregnant, or are breast-feeding.

- experience severe wheezing and difficulty breathing immediately after it is inhaled.
- **6.1.5** Subjects will be instructed not to administer the albuterol and /or study drug on the day of assessments, as the albuterol and/or CsA may complicate the interpretation of the pulmonary function testing.

6.2 Study Drug (Aerosolized Cyclosporine A in solution with Propylene glycol) Administration

6.2.1 Treatment plan:

Week 1: Subjects will receive aerosolized cyclosporine A in solution with propylene glycol using a Sidestream nebulizer with the Invacare Mobilaire compressor at 30 psi. During the first week, subjects will receive 150 mg (total volume 2.4 ml), 3 times weekly. During the first and second doses of 150mg of study drug, subjects will be monitored for correct use of the aerosolizing device under direct supervision of the research team. An individualized maximum tolerated dose may be recommended. **Pediatric dosing** per APT recommendation: During the first week, subjects will receive 150 mg (total volume 2.4 ml), 3 times weekly. Subjects may not initiate aerosolized cyclosporine based on the results of the bronchoscopy, at the discretion of the PI.

Weeks 2-5: Subjects (adults and pediatric) will continue self administration of aerosolized cyclosporine A in solution with propylene glycol 150 mg (total volume 2.4 ml), 3 times weekly. A member of the study team will periodically (during weeks 2-5) call the subjects to discuss any concerns or issues related to study drug administration.

Weeks 6-8: Subjects will undergo a dose escalation to 300 mg inhalation dose (total volume 4.8ml) three times weekly. This is the dose that has been used previously in lung transplant recipients by Iacono et al (8). During dose escalation, subjects will be monitored under direct supervision of the research team. If a subject is unable to tolerate the dose escalation, they will be able to continue at the 150mg dose given three times per week or 125mg (total volume 2.0 mL) daily. **Pediatric dosing** per APT recommendation:

Weight \geq 35 Kg dose at 300 mg (total volume 4.8ml three times weekly).

Weight < 35 Kg dose at 200 mg (total volume 3.2 ml three times weekly). If the subject weighs less than 35 Kg and is unable to tolerate the dose escalation to 200 mg they can continue at 150 mg three times weekly or 85 mg (total volume 1.36 mL) daily.

Weeks 9-18: Continued dosing will be dependent on response and tolerance. Formal PFTs performed at NIH will be obtained to determine response to treatment. Subjects will continue at the 300mg inhalation dose (total volume 4.6ml) three times weekly or maximally tolerated dose.

Any subject that demonstrates disease progression (beginning at week 9) as defined by a 20% or more decline in FEV_1 on two successive measurements at least 2 weeks apart, or >25% increase in existing or addition of new immunosuppressive therapies (sustained for 3 weeks, excluding adjustments made for target drug levels), above baseline levels, due to worsening symptoms related to BOS, will be categorized as a treatment failure and will discontinue study drug administration and proceed with end of study drug assessment. For all others, study drug administration will end at week 19 assessment.

Deviation plan for a missed dose: Subjects will be treated with CIS three times weekly ideally on Monday, Wednesday, and Friday of the week. Should a subject miss a scheduled dose of CIS, we will attempt to alter the dosing regimen for that week so that the subject will still receive three doses of CIS over a week with a limit of 1 dose per day. Data will be captured and reported for subjects who deviate from the treatment plan.

Medication Holds: During study participation, subjects may be instructed to hold administration of CIS after development of an adverse event or other reason at the discretion of the PI. Information pertaining to the reason for and the duration of the medication hold will be captured in the subjects' medical record. If study drug is held for more than 7 days, the time of the hold will not be counted towards the overall study week count. Study drug can be held for up to 12 weeks.

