2.7 Rationale for Dose, Route and Schedule

Most of the previous clinical trials have taken place at the University of Pittsburgh Medical Center (UPMC), which is a leading center in lung transplantation research and clinical management of lung transplant recipients. We will conduct this study using the same dose of CIS as was used in the Pittsburgh chronic lung rejection prevention trial, specifically 300 mg cyclosporine (or maximally tolerated dose up to 300 mg) administered three times per week after an initial 6-week titration period. The formulation is 325 mg cyclosporine in 5.2 mL of propylene glycol (62.5 mg/mL).

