2.9 Rationale for pediatric dosing

(per [name], Chief Medical Officer, APT Pharmaceuticals)

The main safety concerns in this age group are to ensure that there is not excessive systemic exposure to cyclosporine and there is no impact on lung function. It is normal practice to dose the currently licensed forms of cyclosporine (eg Neoral) on the basis of weight and monitor blood levels of cyclosporine. In addition, data from Chua et al, 1994 in 8 children (median age 10.8 y) with cystic fibrosis showed that in this age group, age was not a factor in the amount of drug deposited following aerosol delivery. Therefore, it is proposed to use weight as the main determinant of dose and divide the pediatric population into two groups on the basis of weight. Current experience in the adult population indicates that six adult subjects weighing less than 45 Kg (range 34.5 - 44.3 Kg) have been exposed to CIS. All six achieved a dose of 300 mg in the titration phase and none have reported adverse events associated with study drug. The lightest subject had a peak serum cyclosporine level of 39.7 ng/mL one hour after the inhalation. This level is substantially below the therapeutic level set for systemic therapy (250 -350 ng/mL), suggesting that systemic exposure is not likely to be dose limiting at least in children above 35 kg.

Since the same nebulizer/compressor system will be used in the pediatric population, the proportion of nominal dose which is emitted at the mouth-piece will remain constant. The lung delivered dose is then dependent upon minute ventilation (slightly lower than adults across this age group) and air entrainment (less dilution of the dose due to a lower inspiratory flow rate in children) these factors will exist as a continuum across the population having a greater impact in the smaller younger subjects. Although the adult data suggests that there is a wide therapeutic margin (very low systemic cyclosporine exposure) it would seem prudent to reduce the nominal dose in the youngest, lightest population. The proposed dose for the pediatric age group is as follows:

Weight \geq 35 Kg dose at 300 mg

Weight < 35 Kg dose at 200 mg

This dosing schedule is being used in a multicenter phase III Trial, NCT00755781.

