14.1 Cyclosporine Inhalation Solution (CIS)

Physical, chemical, and pharmaceutical properties CIS is a sterile, clear, colorless, preservativefree solution of cyclosporine (USP) in propylene glycol developed specifically for administration by oral inhalation. The active principle of CIS is a cyclic polypeptide immunosuppressant agent consisting of 11 amino acids. It is produced as a metabolite by the fungus species Beauveria nivea. The molecular formula is $C_{62}H_{111}N_{11}O_{12}$ and the molecular weight is 1202.63.

Chemical name: The chemical name for cyclosporine is [R-[R*,R*-(E)]]-cyclic(L-alanyl-D-alanyl-N-methyl-L-leucyl-N-methyl-L-valyl-3-hydroxy-N,4-dimethyl-L-2-

amino-6-octenoyl-L- α -amino-butyryl-N-methylglycyl-N-methyl-L-leucyl-L-valyl-N-methyl-L-leucyl).

Chemical Structure

Supply: CIS is manufactured and filled into a sterile, single-use clear 6 mL glass vial sealed with a sterilized, siliconized light gray bromobutyl rubber stopper secured by a crimped tear-off aluminum overseal. This container closure system provides protection of the formulation from microbial contamination, moisture ingress, and other environmental contaminants during storage. Each vial contains 5.2 mL of solution containing 325 mg cyclosporine. This vial contains a sufficient amount of cyclosporine, USP in propylene glycol, USP to deliver 300 mg in 4.8 mL. CIS is designed specifically for aerosol inhalation via a single use SideStream[®] disposable nebulizer (Respironics, Inc., Murrysville, PA) with the Mobilaire compressor (Invacare, Elyria, OH) at 30 psi. Previous studies have used the AeroTech[™] II nebulizer with a high flow compressor such as the Sunrise DeVilbiss 8650D set at 40 pounds per square inch (PSI). At 40 PSI, the average flow rate from the compressors is approximately 12.5 L/min.

Storage: CIS vials should be stored in the upright position at controlled room temperature at controlled room temperature, 25°C (77°F), excursions permitted to 15°-30°C (59-86°F). Do not store in the refrigerator or freezer. CIS vials are single use. Any remaining CIS in the vial after dosing should be discarded.

| Component | Quality Standard | Function | Amount per vial | Concentration (% w/vol) |
|------------------|---------------------|-------------------|-----------------|----------------------------|
| Cyclosporine | USP | Active ingredient | 325 mg | 62.5% |
| Propylene Glycol | USP | Solvent | 5.2 mL | - |

Drug Product Composition

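### Section 6.2.1 prints 4.6 mL for the 300 mg dose in weeks 9–18; at the stated concentration the volume should be 4.8 mL (minor)

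*Combined protocol and SAP*

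**What the plan says.** Section 6.2.1 sets out dosing in blocks of weeks. Under weeks 6–8, adults escalate to 300 mg, with 4.8 mL as the volume. Pediatric subjects follow weight: for those at or above the cut-off, "35 Kg dose at 300 mg (total volume 4.8ml three times weekly", and for lighter children, "Weight < 35 Kg dose at 200 mg (total volume 3.2 ml three times weekly". Under weeks 9–18 the section reads: "Subjects will continue at the 300mg inhalation dose (total volume 4.6ml) three times weekly or maximally tolerated dose". That block has no separate pediatric line.

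Two other sections fix the relation between dose and volume. Section 2.7 states: "The formulation is 325 mg cyclosporine in 5.2 mL of propylene glycol (62.5 mg/mL". Section 14.1 describes the same vial and says that its content is enough "to deliver 300 mg in 4.8 mL".

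**The concern.** One dose carries two different volumes within one section, so at least one volume is wrong. The error lies in the maintenance block, the ten weeks before the week 18 response assessment. Section 9.2.4 also repeats pharmacokinetic sampling in week 9 in escalated subjects.

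The volume is not fixed by the packaging. The vial holds 5.2 mL, so a 300 mg dose leaves solution behind whether 4.8 mL (0.4 mL left) or 4.6 mL (0.6 mL left) is drawn up, and section 6.2.2 has the remainder discarded. Emptying the vial therefore does not correct the mistake. Section 6.1.2, which section 6.2.2 applies to the study drug, instructs subjects: "Carefully measure medications exactly as you have been instructed and put them into the nebulizer cup". A wrong volume in the protocol could pass into those instructions and give slightly less than the intended dose. Section 6.2.1 also says that departures from the treatment plan will be captured and reported. With two volumes printed for one dose, it is unclear which one complies.

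**Working it through.** **Inputs**
- Vial content: 325 mg in 5.2 mL (sections 2.7 and 14.1).
- Dose-volume pairs as printed in section 6.2.1.

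**Concentration.** 325 mg / 5.2 mL = 62.5 mg/mL. This reproduces the figure printed in section 2.7.

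**Check of each pair**, using mg held = volume × 62.5:

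| Stated dose | Printed volume | mg held at 62.5 mg/mL | Fits? |
|---|---|---|---|
| 150 mg (weeks 1–5) | 2.4 mL | 150 | yes |
| 300 mg (weeks 6–8) | 4.8 mL | 300 | yes |
| 125 mg daily (fallback) | 2.0 mL | 125 | yes |
| 200 mg (under 35 kg) | 3.2 mL | 200 | yes |
| 85 mg daily (fallback, under 35 kg) | 1.36 mL | 85 | yes |
| 300 mg (weeks 9–18) | 4.6 mL | 287.5 | **no** |

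**Correct volume.** 300 mg / 62.5 mg/mL = 4.8 mL.

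**Size of the error.** 300 − 287.5 = 12.5 mg per dose; 12.5 / 300 = 4.2%.

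**Could 4.6 mL be right on other grounds?** It would need a concentration of 300 / 4.6 = 65.2 mg/mL, which appears nowhere in the protocol. The composition table in section 14.1 labels the concentration as 62.5%, but the 325 mg and 5.2 mL in the same table again give 62.5 mg/mL, so the table does not support 4.6 mL. No change of formulation and no planned reduction at week 9 is described, and the sentence itself still names 300 mg.

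**The pediatric dose in the same sentence.** Four pieces of text bear on it:
1. Weeks 6–8 put a child under 35 kg on 200 mg (3.2 mL).
2. Section 2.9 gives the same weight rule without a time limit, because "it would seem prudent to reduce the nominal dose in the youngest, lightest population".
3. The weeks 9–18 block is about continuing a dose already reached; it describes no second escalation.
4. The weeks 6–8 block also opens with a general sentence naming 300 mg, and its specific pediatric line overrides that sentence for light children. The same reading carries over to the next block.

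Together these keep a child under 35 kg on 200 mg.

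**The case against.** Four objections deserve an answer.

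*Nobody would act on the wrong figure.* By week 9 each escalated subject has been taken through the 300 mg dose under direct supervision, with 4.8 mL as the printed volume, and is told to carry on. No document says that patient instructions are drawn from the weeks 9–18 sentence. This stands in part: an actual underdose is possible, not established.

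*The amount is trivial.* The protocol accepts 150 mg three times weekly or 125 mg daily as adult fallbacks, and keeps in the primary analysis those who tolerate only 150 mg. Section 6.1.2 also expects a little medication to remain in the cup. This stands, and it is why the point is minor. It does not make the printed figure right.

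*It may be a misread digit.* The two volumes differ by one character, and a text copy of a PDF can confuse 6 with 8. Nothing points to that here, and a look at the printed page settles it.

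*The sentence is worse than a typo, because it moves light children to 300 mg.* A reader might infer this from the missing pediatric line, and might add that the fallback to a maximally tolerated dose does not supply 200 mg, since section 2.7 uses that term as a tolerance limit: "300 mg cyclosporine (or maximally tolerated dose up to 300 mg) administered three times per week". The remark about the term is fair. The inference of a 1.5-times dose (300 / 200) is not supported, because a child on 200 mg cannot *continue* at 300 mg and the rule in section 2.9 has no end date. What remains is that the sentence leaves the reader to work this out.

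**Conclusion.** The volume printed for weeks 9–18 is wrong. It should be 4.8 mL; 4.6 mL holds 287.5 mg, 12.5 mg or 4.2% below the stated dose. This rests only on the concentration in section 2.7, which the vial content in section 14.1 and the other five dose-volume pairs in section 6.2.1 confirm.

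The point is minor. It does not touch the sample size, the power or the response rule. It is still worth correcting, because it is an operative dosing instruction for the final ten weeks before the primary endpoint and the volume is measured by hand.

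The absence of a pediatric line in the same sentence is at most a matter for clarification. The documents do not support a claim that children under 35 kg would be dosed at one and a half times the intended amount, nor that a dose reduction at week 9 was planned.

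**What to change.** In section 6.2.1, weeks 9–18, change 4.6 mL to 4.8 mL.

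Optionally, reword the sentence so that the pediatric dose need not be inferred:

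> Subjects stay on the dose reached in weeks 6–8, three times weekly: 300 mg (4.8 mL), or 200 mg (3.2 mL) for pediatric subjects under 35 kg. Those who could not tolerate escalation stay on their fallback regimen.

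Any dosing sheets or patient instructions should be checked for the 4.6 mL figure at the same time. The cost is one figure, or one sentence, of protocol wording; no new visits, procedures, analyses or patients are needed.

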6.2.2 Special Instructions Regarding the Administration of Aerosolized Cyclosporine A

Subjects will follow nebulizer instructions (section 6.1.2) with the following instructions specific to CsA: Continue the treatment until the medication is gone (approx. 20-30 minutes for cyclosporine).

A new nebulizer should be used after albuterol administration. Aerosolized CsA is provided in single use vials. Any CsA remaining in the vial after administration should be discarded immediately.

Aerosolized CsA should be administered such as to avoid others being exposed to CsA during the inhalation process.

Subjects will be given a medication log and asked to record their CIS administration on the log. Subjects will be encouraged to capture this information, but failure to comply with this request will not be reported as a protocol deviation.

6.2.3 Permitted Concomitant Medications

Post Transplant Medications: Subjects that require an increase in existing immunosuppressive meds by 25% due to worsening BOS symptoms (sustained for 3 weeks, excluding adjustments made for target drug levels) or need addition of new immunosuppressive therapies (sustained for 3 weeks), above baseline levels, due to worsening lung disease or BOS symptoms after week 9 will be categorized as treatment failures. However, if the increase or addition of new immunosuppressive therapies is for GVHD not involving the lung or to maintain baseline drug levels, this data will be captured and the subject will continue on study. Efforts will be made to make no changes in existing medical therapies other than tapering immunosuppressants in subjects who have PFTs showing stable or improved pulmonary function.

Systemic immunosuppressants will be tapered beginning at week 6, if subjects have an improvement or stabilization of FEV_1 compared to study baseline values, at the discretion of the PI, taking into account the subject's other manifestations of GVHD. Attempts will be made to taper prednisone first, before other systemic immunosuppressants. Prednisone will be decreased by 25% at the first taper. Subsequent tapers will be at the discretion of the PI. Lung transplant recipients will not have systemic immunosuppressants tapered.

Subjects that have improvement or stabilization of FEV_1 , are not on prednisone, and are only on calcineurin inhibitors, will have their steady state calcineurin inhibitor (systemic cyclosporine or tacrolimus) dose tapered at the discretion of the PI. The calcineurin inhibitor dose will be decreased by 25% at the first taper. Subsequent tapers will be at the discretion of the PI.

Lung Infection Prophylaxis:

Lung infection prophylaxis will be at the discretion of the PI, taking into account the patient's other concomitant medications and medical history. The following are guidelines:

- For PCP pneumonia prophylaxis, subjects will take Bactrim, one double strength tablet (800/160mg) orally three times weekly or aerosolized pentamidine 300mg every four weeks by inhalation.
- For antiviral prophylaxis, subjects will receive acyclovir 800 mg twice daily. Pediatric subjects less than 40kgs will receive acyclovir 20mg/kg po twice daily to a maximum dose of 800mg twice daily.
- For antibacterial prophylaxis, subjects will receive penicillin 500mg twice daily or for penicillin allergic patients, azithromycin 250mg daily.
- Subjects who are already on adequate, alternative prophylaxis agents prescribed by their primary transplant teams can remain on their prior regimens.

6.2.4 Concomitant Medications of Concern with CsA (concurrent use will be per PI discretion and carefully monitored)

- Due to potential for drug interactions, other short acting sympathominetic aerosolized bronchodilators, beta-adrenergic receptor blocking agents, digoxin, monoamine oxidase inhibitors or tricyclic antidepressants will be allowed per PI discretion.
- Due to the potential for compromising the primary endpoint, subjects requiring an increase in systemic immunosuppression or who initiate new immunosuppressive agents, such as oral tacrolimus, CSA, prednisone, mycophenolate mofetil (MMF) or azathioprine due to symptoms of GVHD *not* involving the lung, will remain on study and will have concurrent use of these medications carefully tracked and accounted for during and at the end of study data analysis.
- Cyclosporine can interfere with or be affected by multiple drugs due to its metabolism through the CYP3A4 enzyme. As such, patients who are taking medications, which are either substrates for inducers of, or inhibitors of CYP3A4 (i.e. oral cyclosporine) will be closely monitored (see appendix c).

